4.13.5 Analyses prior to end of scheduled follow-up visits

Any analyses conducted prior to the end of the scheduled follow-up visits should not compromise the integrity of the trial in terms of participant retention or safety or efficacy endpoint assessments.

4.13.6 Specific approach for assessing PE, PE10, PE30

Primary objective 2 is addressed based on comparing cumulative HIV-1 incidence between the group of participants assigned to receive the VRC01 mAb (at either dose pooling over the two doses) and the group of participants assigned to the control group, and secondarily between each individual mAb dose group and the control group. For each prevention efficacy parameter PE, PE10 and PE30, point and 2-sided 95% CI estimates will be reported, along with the 2-sided p-values for testing the respective null hypotheses (with 2-sided p = 0.05 the threshold for a significant effect). Unadjusted and Holm-Bonferroni p-values will be reported for testing of the secondary endpoint efficacy parameters PE10 and PE30.

4.13.7 Assessment of individual-level markers of VRC01 mAb that correlate with protection against HIV infections (Secondary objective 1)

Secondary objective 1 is addressed based on the measurement of VRC01 mAb markers over time in mAb group breakthrough HIV-1–infected cases and in a random sample of HIV-1–uninfected mAb group participants (marker subset), integrated with the genotypic and phenotypic sieve analysis of breakthrough HIV-1 viruses accounting for knowledge of the VRC01 antibody footprint. The main analyses of the secondary objective 1 pool over the two mAb doses to maximize statistical power.

The design and results requirements for successful identification of correlates of protection in secondary objective 1 are:

- 1. Sufficient sample size to observe enough participants diagnosed with incident HIV-1 infection during the primary follow-up period of 80 weeks postenrollment in the mAb arms
- 2. A result of significant beneficial overall mAb PE > 0%
- 3. Sufficiently frequent HIV-1 testing schedule and accurate HIV-1 diagnostics
- 4. Wide variability in the concentration and effector functions of the mAb over time and/or individuals, and the ability to measure these characteristics such that their timing relative to the timing of HIV-1 acquisition is estimated with adequately low measurement error
- 5. mAb marker sampling design that allows sufficiently accurate PK modeling of mAb characteristics over time

Note that the serum concentration mAb markers (secondary endpoints 2) are defined without reference to a particular HIV-1 Env sequence. The effector function markers (also secondary endpoints 2) are relative to specific HIV-1 Envs or panels of Envs, and thus may be linked to immunogenicity endpoints (and the antigen reagents for those endpoints) that would be used in future trials of candidate HIV-1 vaccines. Correlates of protection analyses directly assess how mAb PE depends on markers.

4.13.7.1 Sampling of mAb markers

Characteristics of the mAb or immune responses to the mAb are measured in participants assigned to the mAb treatment groups, and in a small number of participants assigned to the control group. The sampling design determining the set of participants for measuring the markers will be finalized after the primary analysis results. This sampling design will include measuring the markers in all mAb group primary endpoint cases with a minimal number of samples available prior to diagnosis of HIV-1 infection, and on a random sample of participants from each mAb group who complete follow-up to the Week 96 visit HIV-1 negative (mAb group control participants). The random sample of HIV-1 uninfected controls is chosen to create a common control:case ratio across participant strata defined by factors such as dose group, infusion adherence, and calendar period of

enrollment. For participants assigned to the control group, a smaller number of cases and HIV-1 negative controls will be sampled for measurement of markers. The timing of marker measurements is as follows:

- mAb group and control group cases: visits every 4 weeks up until the time of HIV-1 diagnosis and Day 61 (5 days post second infusion) if before diagnosis, plus the first positive visit and additional time-points post HIV-1 infection
- mAb group and control group marker subset controls: visits every 4 weeks through Week 80 plus Day 61 and Weeks 88 and 96

The Day 5 post-second infusion visit is included because it occurs shortly after the end of the distributive phase of the mAb, which together with the samples drawn just before infusions (Week 0, 8, ..., 72), the samples drawn 4 weeks post-infusions (Week 4, 12, ..., 76), and the Week 80, 88, and 96 samples 8–24 weeks post last infusion constitute the basis for modeling marker curves over time.

4.13.7.2 Overview of the analysis of a mAb marker as a correlate of protection

A correlates of protection statistical analysis plan will be finalized not using any information on case-control status of participants; this plan will contain details of the statistical analysis. We provide a brief summary here. For a given mAb recipient, let S(t) be a marker characteristic at time t postenrollment in days, for example the time-concentration curve. The entire curve S(t) cannot be known exactly given that the marker is measured at a grid of time-points. A PK model will be used to express S(t) as a function of the measured marker readouts and error terms. One approach to the correlates of protection analysis will estimate the "prevention efficacy curve" PE(S(t) = s) defined as

 $PE(S(t) = s) = [1 - (hazard-mAb(S(t) = s))/(hazard-control(S(t) = s))] \times 100\%$

where hazard-mAb(S(t) = s) is the hazard rate of HIV-1 infection at time t for a participant assigned to either mAb group with S(t) = s and hazard-control(S(t) = s) is the hazard rate of HIV-1 infection at time t for a participant assigned to the control group who would have had S(t) = s had s/he been assigned to the same mAb group (thus S(t) is a counterfactual random variable for control recipients). Similar parameters are used for assessing time-dependent correlates of protection in vaccine efficacy trials. A time-dependent parameter is used because interest centers on understanding how the current value of a mAb marker associates with the level of instantaneous PE given exposure with an HIV-1 virus at that time. The statistical analysis plan will describe the methods used to estimate PE(s) over the range of values s of a mAb marker characteristic. In addition to estimation, hypothesis testing will be performed to assess whether a mAb marker modifies PE, ie, testing

H0: PE(S(t) = s) = PE versus H1: PE(S(t) = s) varies in s. (1)

Rejecting H0 in favor of H1 supports the role of the marker in protection. The correlates of protection analysis pools over the two mAb groups, for the purpose of improving power both through a larger sample size and through greater inter-individual variability of the mAb markers. Given that the exact dates of infusions have a major impact on mAb markers S(t) such as concentration over time (eg, notice the profound influence of missed

infusions on S(t) in Figure 2-9, the analysis accounts for the exact dates of infusions that are expected to show considerable heterogeneity across trial participants.

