4.13.7.3 A time-window approach to assessing mAb correlates of protection

To explain the concept of this approach, first suppose all participants received all scheduled infusions and rigidly followed the visit schedule. Then this approach compares HIV-1 incidence during the first 4 weeks of the infusion intervals (ie, weeks 1-4, 9-12, 17-20, ..., 73-76) to HIV-1 incidence during the second 4 weeks of the infusion intervals (ie, weeks 5-8, 13-16, 21-24, ..., 77-80), aggregating over the ten 8-week infusion intervals. Because the mAb has much higher concentration during the first halves of the infusion intervals compared to the second halves (eg, demonstrated in Figure 2-9), detection of higher HIV-1 incidence in the second halves of visit windows would imply that higher concentrations are associated with a lower rate of HIV-1 infection.

However, because of missed infusions and the heterogeneity among participants of infusion dates (which is allowable as specified by broad visit windows), a better approach accounts for the set of exact infusion dates of each participant. As such, our approach to implementing the time-window approach compares the mean time between the last infusion and infection for VRC01 group cases, with the mean of the participant-specific weighted average time between infusions of VRC01 group control participants, where the weights allow for changing HIV-1 incidence over time. The analysis stratifies by the 10 mg/kg and 30 mg/kg dose groups and aggregates estimates over these two dose groups. In addition, an important element of the analysis uses predictions of the HIV-1 infection times for all VRC01 group cases. Models for these predictions are built using information on HIV-1 diagnostic tests, intra-host diversity of HIV-1 sequences, HIV-1 viral loads, and perhaps other factors. Initial research to build predictors of HIV-1 infection time based on HIV-1 sequence information has been conducted using validation data sets of acutely HIV-1 infected individuals [127].

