5.3.3 Discontinuing infusions for a participant

Under certain circumstances, an individual participant's infusions will be permanently discontinued. Specific events that will result in stopping a participant's infusion schedule include:

- Co-enrollment in a study with an investigational research agent (rare exceptions allowing for the continuation of infusions may be granted with the unanimous consent of the HVTN 704/HPTN 085 PSRT);
- Clinically significant condition (ie, a condition that affects the immune system or for which continued infusions and/or blood draws may pose additional risk), including but not limited to the following:
 - Any grade 4 local or systemic reactogenicity symptom or AE that is subsequently considered to be related to study product;
 - An SAE that is subsequently considered to be related to study product;
 - Any grade 3 clinical AE (exception: fever or vomiting and subjective local and systemic symptoms) that is subsequently considered to be related to study product;
 - Any grade 3 or 4 lab abnormality confirmed by a repeated value that is subsequently considered to be related to study product;
 - Clinically significant hypersensitivity reaction including but not limited to type 1 hypersensitivity reaction and/or serum sickness associated with study product. Consultation with the HVTN 704/HPTN 085 PSRT is required prior to subsequent infusion following any hypersensitivity reaction associated with study product; or
- Investigator determination in consultation with Protocol Team leadership (eg, for repeated nonadherence to study staff instructions).

Infusions will be permanently discontinued for a participant diagnosed with HIV infection or with 2 reactive HIV tests, even if subsequent testing indicates that the participant is not HIV infected.

Participants for whom infusions are discontinued for reasons other than HIV infection should be counseled on the importance of continuing with the study and strongly encouraged to participate in Schedule 4 follow-up visits and protocol-specified procedures (see Appendix I and Appendix M), unless medically contraindicated.

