¹ Visit #.X indicates a Redraw visit where # is a Schedule 1 visit number. Confirmatory draw for HIV diagnostics will be collected at the Redraw visit. The Redraw visit should occur as soon as possible after the clinic receives a Redraw Request from the HIV diagnostics laboratory. Multiple Redraw visits may be necessary; only the blood specimens indicated in Appendix H will be collected at the subsequent Redraw visits.

² Date of diagnosis = date of the initial specimen draw that led to the first Redraw Request

³ For specimen collection requirements, see Appendix H.

⁴ Includes assessment of HIV/AIDS-related conditions.

⁵ For participants capable of becoming pregnant, pregnancy test may be performed on urine or blood specimens.

Appendix M Schedule 4—Procedures at CRS for participants who discontinue infusions for reasons other than HIV infection

		-	-	-	-	-	-	
Visit Number:	71	72	73	74	75	76	77	78
Days after enrollment:	56	140	224	308	392	504	616	728
Weeks after enrollment:	8	20	32	44	56	72	88	104
Study procedures ¹								
Abbreviated physical exam	х	х	х	х	х	х	х	_
Complete physical exam	-	_	_	_	-	-	-	Х
Risk reduction counseling	Х	х	х	х	х	х	х	х
Concomitant medications	х	Х	Х	х	х	х	х	Х
Intercurrent illness/adverse experience	х	Х	Х	х	х	х	х	Х
HIV infection assessment ²	х	Х	Х	х	х	х	х	Х
Confirm HIV test results provided to participant ³	х	Х	Х	х	х	х	х	Х
Behavioral risk assessment questionnaire	-	Х	_	х	-	х	-	Х
Social impact assessment	Х	Х	Х	х	х	х	х	Х
Local lab assessment ¹								
Urine dipstick ⁴	х	_	_	_	-	-	х	_
Pregnancy test⁵	х	_	х	_	х	-	х	_

¹ For specimen collection requirements, see Appendix I.

² Includes pre-test counseling and HIV testing. A subsequent follow-up contact is conducted to provide post-test counseling and to report results to participant.

³ If HIV test results are not available at the visit indicated, provide test results at next available opportunity.

⁴ And microscopy if needed.

⁵ For participants capable of becoming pregnant, pregnancy test may be performed on urine or blood specimens.

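### Correlates controls must complete a Week 96 visit that participants who stopped infusions do not have, although their infections count as cases; this biases the comparison towards low concentration going with infection

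*Protocol*

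**What the plan says.** Protocol 4.13.7.1 sets two sampling rules for the marker study behind secondary objective 1. For cases, the design includes "measuring the markers in all mAb group primary endpoint cases with a minimal number of samples available prior to diagnosis of HIV-1 infection". For controls, it takes a "random sample of participants from each mAb group who complete follow-up to the Week 96 visit HIV-1 negative", with markers measured at "visits every 4 weeks through Week 80 plus Day 61 and Weeks 88 and 96". The next sentence aims for a "common control:case ratio across participant strata defined by factors such as dose group, infusion adherence, and calendar period of" enrollment. The sampling design "will be finalized after the primary analysis results", and SAP section 4 leaves the correlates cohorts to a separate Correlates of Prevention Efficacy SAP.

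Protocol 5.3.3 says that participants whose infusions are stopped for reasons other than HIV infection are "strongly encouraged to participate in Schedule 4 follow-up visits". Appendices I and M give the Schedule 4 visits as Weeks 8, 20, 32, 44, 56, 72, 88 and 104. SAP Table 1 counts a Schedule 4 infection as a primary endpoint if it is diagnosed on or before a hypothetical Week 80 visit, set at Day 560.

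The time-window analysis (Protocol 4.13.7.3) compares the mean time from last infusion to infection in cases "with the mean of the participant-specific weighted average time between infusions of VRC01 group control participants". A companion analysis does the same with VRC01 concentration.

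**The concern.** Both contrasts need controls that represent the mAb recipients who were at risk when the cases were infected. Under the Week 96 rule, time spent off infusions, with little or no VRC01, can enter through the cases but not through the controls. Cases then look as if they had longer times since infusion and lower concentrations, even where neither is related to risk.

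The protocol expects some cases off infusions: 4.13.7.7 plans a sieve analysis restricted to mAb cases infused at the start of the interval of diagnosis. Sections 4.13.7.1 to 4.13.7.3 contain no matching restriction. The opening of 4.13.7 describes the marker subset simply as a random sample of uninfected mAb participants, without a Week 96 condition. At stake is how strongly concentration appears to correlate with protection. The primary efficacy analysis is not affected.

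**Working it through.** **The rules side by side**

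| Participant | Can be a case? | Can be a control, read literally? |
|---|---|---|
| Schedule 1, infusions on time | Yes | Yes, if negative at Week 96 |
| Schedule 1, some infusions missed | Yes | Yes, if negative at Week 96 |
| Schedule 4, infusions stopped | Yes, up to Day 560 and with enough samples | No; the schedule has no Week 96 visit |

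**The plan's own figure**

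Protocol 4.6.4 expects 37 control and 30 pooled mAb endpoints at PE = 60%, and 4.13.7.5 uses 30 cases and 150 controls. With yearly hazard h, dropout d = 0.10 and τ = 80/52 years, expected events are n·h·[1 − exp(−(h+d)τ)]/(h+d).

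- Control: 900 × 0.03 × [1 − exp(−0.13 × 80/52)]/0.13 = 37.6.
- mAb, with h = 0.4 × 0.03 = 0.012: 1800 × 0.012 × [1 − exp(−0.112 × 80/52)]/0.112 = 30.5.

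Both reproduce.

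**Simulation with no true association**

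- 1.5 million mAb recipients, infection at 1.2% per year whatever the concentration, dropout 10% per year (Protocol 4.6.1).
- On infusions, the Low zone covers 50% of person-time at 10 mg/kg and 10% at 30 mg/kg (Protocol 4.13.7.5), placed at the end of each 8-week interval. More than 8 weeks after the last infusion counts as Low, because 8 weeks is about four half-lives (Protocol 2.4.2).
- Infusion stopping is an assumption: r = 2.5%, 5%, 10%, 15% or 20% per year. The share stopping by Week 72 is 1 − exp(−r × 72/52); for r = 10% this is 12.9%.
- 4,000 replicates of 30 cases and 150 controls, not stratified by adherence. Controls were negative through Week 96 and either still on Schedule 1 (S1) or on either schedule (S1+S4).
- The test is a two-sided 5% comparison of the proportion in the Low zone.

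| Stop by Week 72 | Low, cases | Low, S1 controls | OR, S1 | Rejects, S1 | OR, S1+S4 | Rejects, S1+S4 |
|---|---|---|---|---|---|---|
| 3.4% | 31.3% | 30.0% | 1.06 | 5.6% | 1.01 | 4.6% |
| 6.7% | 31.9% | 30.1% | 1.09 | 6.0% | 1.00 | 4.8% |
| 12.9% | 34.3% | 29.9% | 1.23 | 8.2% | 0.99 | 4.6% |
| 18.8% | 36.2% | 30.0% | 1.33 | 11.0% | 0.97 | 5.5% |
| 24.2% | 38.2% | 30.1% | 1.43 | 15.6% | 0.98 | 5.1% |

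Odds ratios come from unrounded shares; as an example, the 6.7% row gives (0.319/0.681)/(0.301/0.699) = 1.09. S1 controls stay near (50% + 10%)/2 = 30% Low at every stopping rate, so the bias comes wholly from the cases. With essentially no stopping, the S1 rule gives an odds ratio of 0.98 and rejects in 4.8%.

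Mean time since last infusion rises from 4.5 to 7.6 weeks in cases down the table, against 4.0 weeks in S1 controls. With S1+S4 controls it is 4.5 to 7.8 weeks. At 12.9% stopping, 6.5% of cases are more than 8 weeks past their last infusion, which is about 2 of 30.

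**The case against.** **The rule is provisional, and the cohort definitions are in a document that is not available.** This stands. A reader might infer that the final analysis has a false correlate built in; the documents do not show that. They show what the protocol text would do if carried over.

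**Completing follow-up to Week 96 could mean duration of negative follow-up.** A Schedule 4 participant negative at Week 104 might then qualify. That reading is possible, but the control marker list asks for a Week 96 sample that Schedule 4 does not collect, so the wording needs settling either way.

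**Control sampling is stratified by infusion adherence.** Missing an infusion does not by itself move anyone to Schedule 4, so low-adherence Schedule 1 controls exist. This stands in part: stratification could reduce the figures above, which assume none. It cannot supply controls for people who stopped, and weights cannot repair a zero sampling probability.

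**Some Schedule 4 cases may drop out of the case set.** Their visits are 12 to 16 weeks apart, and the minimal number of samples is not defined. How many would qualify is unknown.

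**The simulated null is artificial.** It keeps 60% efficacy in people long off antibody. Protocol 4.13.7 also makes PE significantly above 0% a requirement for identifying a correlate. If VRC01 works, people off infusions should truly be at higher risk, so the bias mostly exaggerates a real association.

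**Much larger effects can be obtained from mean time since infusion.** A one-sided 2.5% test on these means rejects in 5.6%, 12.0% and 21.4% of simulated trials at 10%, 15% and 20% stopping, against at most 0.3% with at-risk controls. That contrast should not be relied on: with sound sampling the test is far below its nominal level.

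**Loss to follow-up.** At 10% per year, 1 − exp(−0.1 × 96/52) = 16.9% are lost before Week 96. Loss unrelated to concentration does not produce this bias.

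**Conclusion.** The concern holds for the protocol text read literally. People who stopped infusions can be cases but not controls, and the bias runs towards low concentration appearing to go with infection. It exaggerates a correlate of protection; where concentration has no relation to risk, it could mimic one.

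The effect is small if up to about 7% stop by Week 72 (odds ratio at most 1.09, rejection about 6%) and becomes material from about 13% (1.23 and 8%, rising to 1.43 and 16% at 24%). These figures rest on an assumed stopping rate unrelated to HIV risk, unstratified sampling, and no loss of Schedule 4 cases through the minimal-sample rule. The nearest documented figure, the SAP 9.5 standard of 90% of infusions received with 70% as the minimum acceptable, measures something different. The documents do not support saying that every off-infusion participant is certainly excluded, or that a correlate would be created from nothing.

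**What to change.** In Protocol 4.13.7.1 and the Correlates SAP, draw controls from all MITT mAb recipients at risk, by case-cohort sampling or by risk-set sampling at each case's estimated infection time, whatever their schedule. At the least, admit mAb recipients HIV-1 negative through Week 80 in any schedule; for Schedule 4, which has no Week 80 visit either, this could be shown by a negative test at Week 88 or later. Use sampling weights, define the adherence strata so that each one containing cases has eligible controls, and apply the same infusion-status rule to cases and controls. Keep the 5:1 ratio. Assay the Week 88 and 96 samples wherever they exist, because 4.13.7.1 relies on them for modelling marker curves, but do not make them a condition of eligibility.

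The number of assays does not change, and Appendix I already stores serum at every Schedule 4 visit. The cost is shorter or sparser marker series for some controls, and so less precise concentration modelling for them.

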4.13.7.3 A time-window approach to assessing mAb correlates of protection

To explain the concept of this approach, first suppose all participants received all scheduled infusions and rigidly followed the visit schedule. Then this approach compares HIV-1 incidence during the first 4 weeks of the infusion intervals (ie, weeks 1-4, 9-12, 17-20, ..., 73-76) to HIV-1 incidence during the second 4 weeks of the infusion intervals (ie, weeks 5-8, 13-16, 21-24, ..., 77-80), aggregating over the ten 8-week infusion intervals. Because the mAb has much higher concentration during the first halves of the infusion intervals compared to the second halves (eg, demonstrated in Figure 2-9), detection of higher HIV-1 incidence in the second halves of visit windows would imply that higher concentrations are associated with a lower rate of HIV-1 infection.

However, because of missed infusions and the heterogeneity among participants of infusion dates (which is allowable as specified by broad visit windows), a better approach accounts for the set of exact infusion dates of each participant. As such, our approach to implementing the time-window approach compares the mean time between the last infusion and infection for VRC01 group cases, with the mean of the participant-specific weighted average time between infusions of VRC01 group control participants, where the weights allow for changing HIV-1 incidence over time. The analysis stratifies by the 10 mg/kg and 30 mg/kg dose groups and aggregates estimates over these two dose groups. In addition, an important element of the analysis uses predictions of the HIV-1 infection times for all VRC01 group cases. Models for these predictions are built using information on HIV-1 diagnostic tests, intra-host diversity of HIV-1 sequences, HIV-1 viral loads, and perhaps other factors. Initial research to build predictors of HIV-1 infection time based on HIV-1 sequence information has been conducted using validation data sets of acutely HIV-1 infected individuals [127].

A related approach to assessing correlates of protection integrates a pharmacokinetic model of the serum concentration of VRC01 over time, comparing the mean VRC01 concentration at the time of HIV infection for VRC01 group cases with the mean of participant-specific weighted average VRC01 concentrations over follow-up time. The participant-specific average VRC01 concentration over follow-up time is intended to reflect the expected concentration at the time of a random HIV exposure, with weighting used as above to allow for changing HIV-1 incidence over time. Details of these statistical methods will be provided in the statistical analysis plan.

4.13.7.4 mAb markers

For effector function markers measured based on a sample from a mAb recipient, the markers are measured to each of a panel of HIV-1 Envelope proteins. The most relevant HIV-1 Env panel represents the VRC01 antibody footprint diversity of viruses exposing trial participants. For example, relevant for the study population of North/South American MSM + TG, Figure 4-8 shows a logo plot of the VRC01 antibody footprint motifs comprising 35 amino acid sites [128,129] based on 276 subtype B US and South American sequences deposited in the Los Alamos National Laboratory (LANL) sequence database between 2006 and 2014. There are 272 unique mAb footprints.

Figure 4-8 Logo plot of the VRC01 antibody footprints that occur in 276 subtype B US and South American sequences deposited in the LANL sequence database between 2006 and 2014

During the conduct of the trial the research team will determine a minimal set of Envs constituting a panel capturing most of the VRC01 mAb footprint diversity of exposing viruses. One effector function marker of interest for assessing as a correlate of protection is the weighted area under the magnitude-breadth neutralization curve of the mAb footprint Env panel, where the weighting is by the estimated prevalence of mAb footprints in HIV-1s circulating at the trial sites during the trial.

For mAb group participants with a primary study endpoint (breakthrough HIV-1 infection during the first 80 weeks), an important marker is the level at which his/her preinfection sample at the time of HIV-1 acquisition neutralizes his/her particular breakthrough virus. (This analysis requires modeling the marker at the time of HIV-1 acquisition based on the available grid of marker measurements.) A result where sera from infected participants generally fail to neutralize their founding viruses would support neutralization as a correlate of protection. This analysis is repeated for other effector functions as a way to discriminate which effector functions are or are not correlates of protection, and to rank the effector functions by their contribution to explaining the level of protection.

